Post-Authorisation Safety Study Protocol

OZAWADE

Study code: P21-02

Title	A multi-center, observational prospective post-authorization safety study to compare the cardiovascular risks and long-term safety of OZAWADE® in patients with obstructive sleep apnoea treated or not by primary therapy and exposed or not to OZAWADE® when used in routine medical practice.
Protocol version identifier	3.0
Date of last version of protocol	23NOV2023
EU PAS register number	Still has to be registered
Active substance	N07XX11, pitolisant (chlorhydrate)
Medicinal product	OZAWADE® 4,5 mg, film-coated tablet
	OZAWADE® 18 mg, film-coated tablet
Product reference	OZAWADE® 4,5 mg, film-coated tablet: EU/1/21/1546/001
	OZAWADE® 18 mg, film-coated tablet: EU/1/21/1546/002
Procedure number	EMEA/H/C/0005117
Marketing authorisation holder(s)	Bioprojet Pharma
	[name]
	[name]
	Phone: +
	www.bioprojet.com
Joint PASS	No
Research questions and objectives	Primary objective
	The primary objective of this study is to demonstrate that OZAWADE® supplementation in obstructive sleep apnoea (OSA) patients does not increase the incidence of cardiovascular events (CVE) compared with OZAWADE® unexposed patients (non-inferiority) and to evaluate the long-term safety of OZAWADE® when used as per SmPC in patients with OSA.

Secondary objective(s) Safety • To evaluate the time to cardiovascular events of interest in OSA patients exposed to OZAWADE® as per SmPC compared with OZAWADE®-unexposed OSA patients. • To evaluate the time to adverse drug reaction (serious and non-serious) in OSA patients exposed to OZAWADE® as per SmPC compared with OZAWADE® unexposed OSA patients. Exploratory objective(s) **Effectiveness** • To evaluate the effectiveness of OZAWADE® through the Epworth Sleepiness Scale (ESS) when used as per SmPC in patients with OSA. • To evaluate the effectiveness of OZAWADE® through the Maintenance of wakefulness test (MWT) when used as per SmPC in patients with OSA. • To evaluate the effectiveness of OZAWADE® through the Multiple Sleep Latency Test (MSLT) when used as per SmPC in patients with OSA. • To evaluate the effectiveness of OZAWADE® through the Fatigue Severity Scale (FSS) when used as per SmPC in patients with OSA. Adherence • To evaluate the adherence to OZAWADE® when used as per SmPC in patients with OSA. • To evaluate the adherence to continuous positive airway pressure (CPAP) / mandibular advancement devices (MAD), between the group of patients exposed to OZAWADE® and the group of patients not exposed to OZAWADE®. Other To evaluate the reduction of car/traffic accidents. Country(-ies) of study 4 countries: France, Italy, Germany and possibly Netherlands, Belgium or Spain **Author** Study Medical Director **Bioprojet Pharma** Tel: + E-mail address:

This protocol was drafted according to Good Epidemiological Practices

Confidential information

The information contained in this protocol is confidential and is intended for the use of Participating physicians.

This document is the property of Bioprojet pharma and should not be – in whole or in part – transmitted, reproduced, published or used without expressed authorisation of Bioprojet Pharma. The information contained in this protocol is confidential and is intended for the use of participating physicians.

Marketing authorisation holder(s)

Marketing authorisation holder(s)	Bioprojet Pharma
	[name]
	[name]
	France
	Phone: +
	www.bioprojet.com
MAH contact person	
	Regulatory Affairs Director
	Tel: +
	E-mail address:

Participation to the study / Confidential agreement

Information contained in this protocol are confidential and are the property of Bioprojet Pharma.

11.1.1. Adverse Event	47
11.1.2. Serious Adverse Event	47
11.1.3. Special Situations	48
11.1.4. Adverse Events of Special Interest	49
11.2. Intensity, causality, expectedness and outcome assessment	49
11.2.1. Intensity Assessment	49
11.2.2. Causality Assessment	49
11.2.3. Outcome Assessment	50
11.3. Expectedness of events	50
11.4. Collection and reporting of AEs, SAEs and SSs	50
11.4.1. Collection of the AEs, SAEs, SSs in the eCRF	50
11.4.2. Reporting of events to Sponsor Pharmacovigilance	50
11.4.3. Regulatory reporting requirements	51
12. Plans for disseminating and communicating study results	53
13. References	54
APPENDIX 1	57

List of Tables

Table 1. Study Milestones	24
Table 2. Schedule of Assessments	29

List	of	Figures	;
	\mathbf{v}		,

2. List of abbreviations

Abbreviations, specific or unusual terms and units used in this study protocol are listed in the Table below:

Abbreviation	Definition
ADR	Adverse Drug Reaction
AE	Adverse Event
AESI	Adverse Event of Special Interest
AHI	Apnoea-Hypopnea Index
ALc	Alcohol Consumption
ARD	Absolute Risk Difference
BDI	Beck Depression Inventory
BMI	Body Mass Index
CABG	Coronary Artery Bypass Graft
ClinRO(s)	Clinician Reported Outcome(s)
CPAP	Continuous Positive Airway Pressure
CRF	Case Report Form
CRO	Contract Research Organisation
CRA	Clinical Research Assistant
CV	Cardiovascular
CVE	Cardiovascular Events
DMP	Data Management Plan
EC	Ethics Committee
ECG	Electrocardiogram
EDC	Electronic Data Capture
EDS	Excessive Daytime Sleepiness
eCRF	electronic Case Report Form
EMA	European Medicines Agency
ESS	Epworth Sleepiness Scale
FSS	Fatigue Severity Scale
FU	Follow-Up
GDPR	General Data Protection Regulation
GVP	Good Pharmacovigilance Practices
HDL	High Density Lipoproteins
ICH	International Council for Harmonisation of Technical Requirements for Pharmaceuticals
ICH	for Human Use
IEC	Independent Ethics Committees
IRB	Institutional Review Boards
LDL	Low Density Lipoproteins
MACE	Major Adverse Cardiovascular Events
MAD	Mandibular Advancement Devices
MedDRA	Medical Dictionary for Regulatory Activities
MMAS-8	Morisky Medication Adherence Scale 8-item
MSLT	Multiple Sleep Latency Test

MWT	Maintenance of wakefulness test
NIM	Non-Inferiority Margin
OSA	Obstructive Sleep Apnoea
PASS	Post-Authorization Safety Study
PI	Package Insert
PT	Preferred Term
PRO(s)	Patient Reported Outcome(s)
RMP	Risk Management Plan
SADR	Serious Adverse Drug Reaction
SAE	Serious Adverse Event
SAP	Statistical Analysis Plan
SD	Standard Deviation
SMH	Smoking Habits
SmPC	Summary of Product Characteristics
SOC	System Organ Class
SS	Special Situation

3. Responsible parties

3.5. Other Investigators

The list of all participating physicians is available upon request as a stand-alone document.

4. Abstract

Title

A multi-center, observational prospective post-authorization safety study to compare the cardiovascular risk and long-term safety of OZAWADE® in patients with obstructive sleep apnoea treated or not by primary therapy and exposed or not to OZAWADE® when used in routine medical practice.

Background and Rationale

Background

Obstructive Sleep Apnoea (OSA) is a highly prevalent chronic disease affecting nearly 1 billion people aged 30–69 years worldwide [1]. Continuous positive airway pressure (CPAP) is the gold-standard first-line treatment for patients with symptomatic OSA. However, a substantial proportion of CPAP-treated OSA patients continue to experience Excessive daytime sleepiness (EDS) despite optimized CPAP therapy.

Pitolisant is a selective histamine H3 inverse agonist/antagonist for treating patients with narcolepsy and has also showed efficacy in OSA patients treated or not with CPAP. Under the trade name OZAWADE®, it has been authorized for use in the EU on July 22, 2021, in adult patients with OSA whose EDS has not been satisfactorily treated by, or who have not tolerated OSA primary therapy, such as CPAP and Mandibular Advancement Devices (MAD).

Rationale

The Risk Management Plan for OZAWADE® identifies some potential risks and missing information about safety. One of the potential risks concerns cardiovascular (CV) events including QT-interval prolongation and the missing information refers to the long-term safety of OSA patient treated with OZAWADE® according to the SmPC.

The Sponsor has agreed with the EMA to conduct a Post-Authorization Safety Study (PASS) as part of the Risk Management Plan (RMP) for OZAWADE®.

Research Question and Objectives

Primary objective

The primary objective of this study is to demonstrate that OZAWADE® supplementation in obstructive sleep apnoea (OSA) patients does not increase the incidence of cardiovascular events (CVE) compared with OZAWADE® unexposed patients (non-inferiority) and to evaluate the long-term safety of OZAWADE® when used as per SmPC in patients with OSA.

Secondary objective(s)

Safety

- To evaluate the time to cardiovascular events of interest in OSA patients exposed to OZAWADE® as per SmPC compared with OZAWADE® unexposed OSA patients.
- To evaluate the time to adverse drug reaction (serious and non-serious) in OSA patients exposed to OZAWADE® as per SmPC compared with OZAWADE® unexposed OSA patients.

Exploratory objective(s)

Effectiveness

- To evaluate the effectiveness of OZAWADE® through the Epworth Sleepiness Scale (ESS) when used as per SmPC in patients with OSA.
- To evaluate the effectiveness of OZAWADE® through the Maintenance of wakefulness test (MWT) when used as per SmPC in patients with OSA.
- To evaluate the effectiveness of OZAWADE® through the Multiple Sleep Latency Test (MSLT) when used as per SmPC in patients with OSA.
- To evaluate the effectiveness of OZAWADE® through the Fatigue Severity Scale (FSS) when used as per SmPC in patients with OSA.

Adherence

- To evaluate the adherence to OZAWADE® when used as per SmPC in patients with OSA.
- To evaluate the adherence to continuous positive airway pressure (CPAP) / mandibular advancement devices (MAD), between the group of patients exposed to OZAWADE® and the group of patients not exposed to OZAWADE®.

Other

• To evaluate the reduction of car/traffic accidents.

Study Design

This is a prospective, observational, multi-center, open-label, long term, cohort study (OZAWADE® exposed and OZAWADE® unexposed) designed to collect data on the long-term safety of OZAWADE® treatment. This study will be conducted in patients with OSA whose EDS has not been satisfactorily treated by, or who have not tolerated OSA primary therapy. The study will be conducted by physicians specialized in sleep management such as sleep specialists, pulmonologists, cardiologists, otorhinolaryngologist and neurologists.

Primary, secondary, and exploratory endpoints

Primary endpoint

The primary endpoint will be the occurrence of at least one cardiovascular event (CVE) or one serious drug related adverse event during the five years of follow up for each participating patient.

Secondary endpoints

The following secondary endpoints will separately investigate each type of event globally appraised by the primary endpoint:

- Time to CVE occurrence and CVE distribution in time according to classification MACE and non-MACE
- Time to Adverse Drug Reaction (ADR)
- Time to Serious Adverse Drug Reaction (SADR)
- Beck Depression Inventory global score at each collection time

Exploratory endpoints

Effectiveness

Change from patient inclusion date to the end of study as evaluated with:

- Epworth Sleepiness Scale (ESS) global score
- Maintenance of wakefulness test (MWT) mean sleep latency
- Multiple Sleep Latency Test (MSLT) mean sleep latency
- Fatigue Severity Scale (FSS) global score

Adherence

- Rate of patients compliant with their OZAWADE® treatment (according to the 8-item Morisky Score) at each visit.
- Rate of patients compliant with their primary therapy (according to the mean number of hours of
 use per night during the last three months) at each visit.

Other

Incidence of car accidents at driving (comparison of answers to the questionnaire "assessment of sleeping at driving" between inclusion and yearly evaluation)

Study Procedures

During the 2-year enrolment phase, 502 patients are planned to be recruited in four to five countries where OZAWADE® is on the market (*i.e.*, France, Germany, Italy and possibly Netherlands, Belgium or Spain), in approximately 8 to 15 centers per country. In each center, participating physicians will enrol all eligible patients consecutively according to a systematic sampling technique (*i.e.*, in chronological order of their arrival at the consultation) irrespective of the treatment decision (i.e. patients prescribed and not prescribed OZAWADE®) until the recruitment target is reached globally in both groups or until the end of the enrolment period. Patients will be followed-up up to 5 years (follow-up visit at six months and then once a year).

Duration of Study

There will be approximately two years of recruitment and five years of follow-up.

Selection of the Patients

Inclusion Criteria

A patient must meet all of the following criteria to be eligible for participation in the study:

- 1. Patients with OSA, treated or not by primary therapy (e.g., CPAP, MAD).
- 2. Patients eligible for treatment by OZAWADE® as per SmPC (being prescribed or not with OZAWADE®).
- 3. Patients naive of treatment with any wake-promoting agent or patients previously treated with wake-promoting agent for less than six months and having discontinued the treatment for at least three months.
- 4. Patient informed about the study and who either did not oppose to their data collection or who signed the Informed Consent Form when applicable.

Exclusion Criteria

A patient who meets the following criterion is not eligible for participation in the study:

- 1. Patient participating in a clinical trial.
- 2. Patient under curatorship or deprived of liberty.

Variables

The data collected will be those data that the investigating centers are used to assess during routine visits, exception made of some Clinician- or Patient- Reported Outcomes (ClinROs, PROs) questionnaires (see below) planned to properly answer to the study objectives. The following assessments have no obligation to be performed and only the available measures and assessments will be collected in the CRF.

Site Selection Questionnaire

To assess potential selection bias of the participating physicians, the country, speciality, age, department and institution type/patient flow will be collected from all physicians contacted during the selection process.

Demographic and Baseline Characteristics

Patient's demographic and baseline characteristics such as the age, gender, socio-professional status, date of OSA diagnosis and relevant medical history will be collected only at study inclusion. Other data (i.e. height and weight, waist circumference, smoking status, current daily alcohol consumption, physical activity, duration of sleep and perceived sleepiness at driving) will be collected both at study inclusion and at each follow-up visits (except for the perceived sleepiness at driving which will not be collected at the 6-month follow-up visit).

Prior and concomitant medications or therapies

- OSA primary therapy: the use of CPAP of alternative therapy (e.g., MAD) will be collected both at study inclusion and at each follow-up visits.
- Prior and concomitant medications: The data on prior medication will be collected only at study inclusion. The data on concomitant medications will be collected both at study inclusion and at each follow-up visits.

Prospective data (collected both at study inclusion and at each follow-up visit)

- Electrocardiogram (ECG) when available, QTcF;
- Blood pressure and heart rate;
- Beck Depression Inventory (BDI), global score (not collected at the 6-month follow-up visit);
- Disease activity:
 - Apnoea-hypopneoa index (AHI);
 - o Epworth Sleepiness Scale (ESS), global score;
 - Maintenance of wakefulness test (MWT) or Multiple Sleep Latency Test (MSLT) (not collected at the 6-month follow-up visit), mean sleep latency;
 - Fatigue Severity scale (FSS), global score (not collected at the 6-month follow-up visit).
- Exposure to OZAWADE® (collected at study inclusion and at the follow-up visit if not started at inclusion);

- Adherence to OZAWADE®: through the Morisky Medication Adherence Scale 8-item (MMAS-8) questionnaire;
- Laboratory assessment: cholesterol, glycemia and triglycedemia (not collected at the 6-month follow-up visit).
- Adverse events and special situation: All AEs, SAEs, Adverse Events of Special Interest (AESI) i.e. cardiovascular events and Special Situations (SS) occurring from each patient's enrolment to the end of the study.

AESIs defined as cardiovascular events based on the following list:

Major Adverse Cardiovascular Event (MACE)

- Acute myocardial infarction;
- o Acute coronary syndrome / ischemic heart disease
- Stroke (ischemic, haemorrhagic);
- Heart failure;
- o Cardiovascular death.

Non-Major Adverse Cardiovascular Events (non-MACE)

- New onset of angina;
- Unstable angina;
- Transient ischemic attack;
- New onset atrial fibrillation;
- Unscheduled interventional cardiology procedure (stenting, CABG);
- New onset hypertension > 140/90 mm Hg (with new hypertension treatment or a posology adjustment of hypertension treatment);
- New onset or worsening of peripheral vascular disease or unscheduled intervention;
- Stent thrombosis;
- QT prolongation (calculated with the electrocardiogram Fridericia's corrected QT interval strictly higher than 450 ms).

Patient Non-Inclusion Log

Data (i.e. age, gender, year of OSA diagnosis, reason for non-participation) collected from eligible patients not enrolled in the study will be collected in such log in order to assess potential selection bias.

Data Sources

This is a prospective, observational study, and patient data collected from the participating physicians will be abstracted from medical records and from administration of baseline and follow-up assessments and questionnaires (PROs and ClinROs).

A yearly blinded review of the adverse events and adjudication of the events (major adverse cardiovascular events [MACE] and non-major adverse cardiovascular events [non-MACE]) will be centrally performed by an Independent Committee.

Sample Size

Data Analysis

Population

In this observational study, all included patients are eligible to the analysis.

Statistical Method

The estimates of the main endpoint will be compared among OZAWADE® users and non-users by a generalized Linear Model featuring Poisson regression. In this model we consider a post stratification model based on fixed covariates combined with a random effect attempting a correction on the expected imbalance due to the non-randomized treatment. Cumulative incidence estimate and Cox proportional Hazard regression will be used as secondary analysis.

Milestones

• Ethics submission: Q2/Q3 2024

Start of data collection: Q3/Q4 2024

• End of data collection: Q4 2030/Q1 2031

• Interim study report: yearly throughout the study

Final report of study results: Q4 2031

5. Amendments and updates

None.

6. Milestones

The planned study milestones, as per Good Pharmacovigilance Practices definitions, are summarized below.

Table 1. Study Milestones

Study Milestone	Planned date
Ethics submission	Q2/Q3 2024
Start of data collection	Q3/Q4 2024
End of data collection	Q4 2030/Q1 2031
Interim study report	Yearly throughout the study
Final report of study results	Q4 2031

7. Rationale and background

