CPAP. In OSA patients with residual EDS, refusing or non-adherent to CPAP, pitolisant significantly reduced self-reported daytime sleepiness and fatigue, and improved patient-reported outcomes and physician disease severity assessment after 12 weeks of treatment [31]. Pitolisant, used as adjunct to CPAP therapy for OSA with residual EDS despite good CPAP adherence, also significantly reduced subjective and objective sleepiness and improved participant-reported outcomes and physician-reported disease severity after 12 weeks [32]. In two dedicated QT studies, supra-therapeutic doses of pitolisant (6-12-times the therapeutic dose, that is 108 mg to 216 mg) produced mild to moderate prolongation of QTc interval (10-13 ms). As reported in the OZAWADE® SmPC, patients with cardiac disease, hypertension, at risk of major adverse cardiovascular events (MACE), co-medicated with other QT-prolonging medicinal products or known to increase the risk of repolarization disorders, or co-medicated with medicinal products that significantly increase pitolisant Cmax and AUC ratio or patients with severe renal or moderate hepatic impairment should be carefully monitored [33].

Clinical studies have not raised any safety concerns and confirmed in OSA patients the favourable safety profile of pitolisant as reported in patients with narcolepsy. Pitolisant, under the trade name OZAWADE®, has been authorized for use in the EU on July 22, 2021, to improve wakefulness and reduce EDS in adult patients with OSA whose EDS has not been satisfactorily treated by, or who have not tolerated OSA primary therapy, such as CPAP.

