anti	Smoking status ³	X ₃	X ³	X ³	X ₃	X ₃	X ₃	X ₃	X ³
Patie	Alcohol consumption	X	х	Х	X	X	X	X	х
	Physical activity	Х	Х	X	X	X	X	X	Х
	Relevant medical history	X							
	Prior medications (last three months)	X							
	Relevant concomitant medications	X	Х	Х	X	X	X	X	Х
e e	Physical examination	X		Х	X	X	Х	X	х
minati	All Adverse Events including adverse events of special interest ⁴		х	х	х	х	X	x	х
l exa	Blood pressure, heart rate	X	Х	Х	X	X	X	X	X
Medical examination	Biological assessment of less than 12 months (cholesterol, glycemia and triglycedemia)	х		х	х	х	х	х	Х
	ECG brought by the patient when available (QT measure) ⁵	X _e	X ⁶	X ⁶	X _e	Xe	Xe	X _e	X _e

PASS protocol Version 3.0 – 23 NOV 2023

PASS Protocol [P21-02/OZAWADE]

OZAWADE

	Procedures /Visits Visit window		FU 6 Months	FU Year 1	FU Year 2	FU Year 3	FU Year 4	FU Year 5	End of study
			6M [3-9M[12M [9-18M[24M [18-30M[36M [30-42m[48M [42-54[60M [54-66[
OSA and sleep history	OSA and sleep history, duration of sleep	X	X ⁷	Х	х	X	Х	Х	Х
	Apnoea-hypopnea index (AHI) At diagnosis of OSA At follow-up visits (with or without CPAP) ⁸	х	х	х	х	х	x	х	х
	Epworth Sleepiness Scale (ESS)	X	X	Х	Х	Х	Х	Х	Х
	CPAP or alternative (e.g., MAD) and adherence ⁹	Х	х	х	х	х	х	х	X
	Maintenance of wakefulness test (MWT) or Multiple Sleep Latency Test (MSLT)	X		х	х	X	х	х	X
	Beck Depression Inventory	Х		Х	Х	Х	Х	Х	Х
	Fatigue Severity scale	X		Х	Х	Х	Х	X	Х
	Assessment of perceived sleepiness at driving	X		х	х	х	х	х	X
OZAWADE* use	Prescription (when applicable)	X							
	Adherence with the Morisky Medication Adherence Scale 8-item (MMAS-8)		х	х	х	х	х	x	х

- 1. Data collected in the CRF will correspond to data collected in routine practice in the investigating centers.
- Height at inclusion visit only.
- 3. Smoking status: in pack-year.
- 4. Adverse events of special interest include the following cardiovascular events: acute myocardial infarction, new onset of angina, unstable angina, stroke (ischemic, haemorrhagic), transient ischemic attack, new onset atrial fibrillation, unscheduled interventional cardiology procedure (stenting, CABG), new onset hypertension (with new hypertension treatment or a posology adjustment of hypertension treatment), new onset or worsening of peripheral vascular disease or unscheduled intervention, stent thrombosis, heart failure, QT prolongation and cardiovascular death.
- 5. ECG when available.
- 6. Last test available at the time of the visit.
- 7. Duration of sleep.

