9.1.2. Primary, secondary and exploratory endpoints

9.1.2.1. Primary endpoint

The primary endpoint will be the occurrence of at least one cardiovascular event (CVE) or one serious drug related adverse event during the five years of follow up for each participating patient.

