9.3.7. Exposure and adherence to OZAWADE®

9.3.7.1. Treatment exposure

Exposure to OZAWADE® will be collected at inclusion and at follow-up visits (if not started at inclusion), with the date of prescription and the prescribed dose.

At each follow-up visit, dose modifications, treatment interruptions and permanent discontinuation will be collected. Reasons of changes will also be collected.

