9.7.5. Primary Analyses

The main objective of the study is to demonstrate that OZAWADE® supplementation does not increase CV events compared with control (non-inferiority). The following analysis will be conducted:

The annual CV morbidity incidence will be estimated by the occurrence of CVE per patient per year equivalent to the proportion of patients with at least one CVE.

The CV risk is known to be higher for OSA patient with existing CV history, using or not CPAP, and well-known risk factors: diabetes, cholesterol, weight, hypertension, demographics (age, gender), lifestyle (fitness, alcohol use, smoking habits).

A generalized linear mixed model featuring Poisson regression will be based on a post stratification model based on the following fixed covariates or random effects:

- nCVE_b, prior CV history measured by the number of CV events experienced before baseline, expected as the essential predicting covariates;
- Risk factors (RF): diabetes, cholesterol, weight, hypertension, alcohol use, and smoking habits reported at baseline;
- Demographics: gender, age, country, study center
- Matched classes propensity clusters: the treatment will be non-randomized but determined by the investigator, involving an expected imbalance between groups on baseline conditions. The decision of prescribing a given medicine will be assumed on a set of baseline covariates defined in the statistical plan. As too many covariates are expected, finding sufficient exact matches is unfeasible, and the goal of subclassification is to form matched subclasses (clusters), such that in each the distribution of covariates for the treated and control groups are as similar as possible. The propensity score will be used as the scalar distance with a two-stage algorithm starting with the nearest neighbour matching and optimized by a full matching procedure [39, 40, 41].

The final model is:

CVE ~ $nCVE_b + \Sigma_i RF_i + gender + age + trt + \{country\} + Offset (log-exp) + \{center | country\} + \{cluster\}$

The notation Σ_i RF_i covers the above mentioned considered risk factors. The obvious effect of the exposure duration is measured by the offset of its logarithm. The last fixed factor is the treatment (trt) binary effect (0=control, 1=pitolisant). Country, site effect nested within country, and cluster (matched group) effects will be used as random factors (between {}).

Sensitivity Analysis

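### The hypertension item counts only when antihypertensive treatment changes, so a rise managed solely by changing OZAWADE goes uncounted, a route open only to exposed patients; a management-independent sensitivity analysis is needed

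*Protocol*

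**What the plan says.** The cardiovascular event list appears in the Abstract (Section 4, Variables) and again in 9.3.10. In both places the hypertension item is "New onset hypertension > 140/90 mm Hg (with new hypertension treatment or a posology adjustment of hypertension treatment". Table 2, note 4 (9.1.1) keeps the treatment condition but drops the threshold: "new onset hypertension (with new hypertension treatment or a posology adjustment of hypertension treatment".

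The item feeds the primary endpoint, defined in 9.1.2.1 as "occurrence of at least one cardiovascular event (CVE) or one serious drug related adverse event during the five years of follow up". The primary model in 9.7.5 is narrower and has CVE as its outcome: "The annual CV morbidity incidence will be estimated by the occurrence of CVE per patient per year". Its aim is to "demonstrate that OZAWADE® supplementation does not increase CV events compared with control (non-inferiority".

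Changes to OZAWADE are recorded under 9.3.7.1: "At each follow-up visit, dose modifications, treatment interruptions and permanent discontinuation will be collected. Reasons of changes will also be collected". No endpoint rule uses this information. Patients who stop OZAWADE remain in follow-up (9.1.3). Blood pressure is taken at each visit and self-measured during the following month with a diary (9.3.4), but outside the event list it is only described by group (9.7.7).

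**The concern.** The item has two conditions: a blood pressure criterion and a change in antihypertensive treatment. The second depends on how the rise is managed, and the management options differ between groups. Where a drug change is made in an unexposed patient, it is to antihypertensive treatment, and the event counts. In an exposed patient the physician, who knows the treatment, may instead change OZAWADE. If nothing else is done and the event is not serious, the blood pressure criterion was met but no CVE is recorded. The patient stays in follow-up and contributes person-time without that event.

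The cases lost this way are those the physician is most likely to attribute to the drug. In a study whose aim is to show no increase in cardiovascular events, a rule that can drop such cases from the exposed group alone deserves a check. The list itself offers a contrast: QT prolongation counts on a measured value (QTcF above 450 ms), whatever is done about it.

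**Working it through.** **Step 1: the rule by group.** Reading 9.3.10 with 9.1.2.1 and 9.3.7.1, a new rise above 140/90 is treated as follows.

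| Handling of the rise | Exposed | Unexposed |
|---|---|---|
| Antihypertensive started or adjusted | CVE | CVE |
| OZAWADE changed only, event not serious | not a CVE | route does not exist |
| OZAWADE changed, antihypertensive follows later | CVE | route does not exist |
| No drug change | not a CVE | not a CVE |
| Serious and drug-related, no antihypertensive change | meets the endpoint in 9.1.2.1, but not the CVE outcome in 9.7.5 | not applicable |

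Only the second row is one-sided without later recovery.

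**Step 2: effect on the ratio.** Let h be the share of exposed patients with a CVE whose only CVE is hypertension. Let f be the share of those managed through OZAWADE alone. Then

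observed ratio = true ratio × (1 − h·f),

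where the true ratio also counts the diverted cases. The multiplier never exceeds 1. The documents give neither h nor f, so both are assumed:

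| h | f = 0 | f = 0.1 | f = 0.2 | f = 0.5 |
|---|---|---|---|---|
| 0.2 | 1.00 | 0.98 | 0.96 | 0.90 |
| 0.4 | 1.00 | 0.96 | 0.92 | 0.80 |
| 0.6 | 1.00 | 0.94 | 0.88 | 0.70 |

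**Step 3: an example with a harmful drug.** Assume 5-year control risks of 15% for treated new hypertension and 10% for other CVEs, without overlap, and a factor of 1.33 on hypertension.

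- True composite ratio: (0.10 + 0.15 × 1.33) / 0.25 = 1.20.
- Excess hypertension: 0.15 × 0.33 = 0.0495. If 25%, 50% or 100% of this excess is diverted, the ratio is (0.25 + 0.0495 × 0.75) / 0.25 = 1.15, (0.25 + 0.0495 × 0.50) / 0.25 = 1.10, or 1.00.

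**Step 4: effect on the non-inferiority error.** The public text shows no margin, alpha or event rate (9.5 and Appendix 1 are empty), so no figure of the plan can be reproduced here. I take 195 per group from 9.9 and assume a one-sided 0.025 Wald test on the log ratio, with the true ratio equal to the margin. For 25% control incidence, margin 1.5, h = 0.4 and f = 0.2:

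- Expected events: 195 × 0.25 = 48.75 in controls and 48.75 × 1.5 × 0.92 = 67.28 in exposed.
- SE = √(1/48.75 + 1/67.28) = 0.188.
- P(false non-inferiority) = Φ(−ln 0.92 / 0.188 − 1.96) = Φ(−1.52) = 0.065, against a nominal 0.025.

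With 251 per group (half of 502) the figure is 0.073. For 195 per group, incidence of 15% to 35% and margins of 1.3 to 2.0:

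| h·f | False non-inferiority |
|---|---|
| 0 | 0.025 |
| 0.04 | 0.036 to 0.046 |
| 0.08 | 0.052 to 0.080 |
| 0.20 | 0.136 to 0.304 |

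These figures isolate one mechanism. They do not forecast the study's error rate.

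**The case against.** A reader might infer that a blood pressure rise handled through OZAWADE can never be a CVE, and that the comparison as a whole is therefore tilted toward non-inferiority. The documents do not support either statement.

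- **Never is too strong.** Follow-up continues after OZAWADE is stopped (9.1.3), so later antihypertensive treatment meets the item. A serious drug-related rise meets the other limb of 9.1.2.1, although 9.7.5 as written models CVE alone. A patient with any other listed CVE counts anyway. The list may also be enlarged (9.3.10), but no rule is given for doing so.
- **Net direction is open.** Section 7.1 singles out patients for careful monitoring ("As reported in the OZAWADE® SmPC, patients with cardiac disease, hypertension, at risk of major adverse cardiovascular events (MACE", among others), and 9.3.3 repeats this. In an open-label study, closer observation of exposed patients could produce more detected rises and more antihypertensive starts, which pushes the ratio up.
- **The documents do not say that OZAWADE will be changed for blood pressure.** Section 9.3.7.1 provides for recording changes of any kind, with reasons. It gives no frequency.
- **The signal is not hidden.** A rise judged related and non-serious is an ADR (11.4.2.1). It enters time to ADR (9.1.2.2) and the tables of related AEs by group (9.7.7).
- **A treatment condition has a purpose.** Where assessments follow routine care and none is obligatory (9.3), it makes the event more specific. It also leaves rises that prompt no drug change uncounted in both groups.

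All of this stands. It limits the claim, but it does not remove the one-sided route. Blinded adjudication (9.4) does not close it either, because no rule is given for counting such a rise.

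**Conclusion.** The point holds as a one-sided counting rule of unknown size. All three statements of the item require a change in antihypertensive treatment, and no text counts a non-serious rise managed only by changing OZAWADE. Taken alone, this can only lower the exposed event count and so favours non-inferiority. Under the assumed ranges the multiplier on the ratio runs from 0.98 down to 0.70, and it is exactly 1.00 if f = 0. Every one of these inputs is an assumption. The example in Step 3 also takes the components as non-overlapping and assumes that no diverted case is treated later, both of which enlarge the effect.

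Net bias across all mechanisms is not established. The documents therefore do not support saying that the primary result will be biased, and they do not justify redefining the primary item. They do support checking whether the non-inferiority conclusion depends on the treatment condition, using data the study already plans to collect.

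**What to change.** Keep the primary item as defined. In 9.7.5, add:

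1. A prespecified sensitivity analysis of the primary model in which the hypertension item is met by new-onset blood pressure above 140/90 at a study visit, confirmed by that visit's home diary where available, regardless of management. Apply the same rule in both groups.
2. A count by group of rises above 140/90 recorded as the reason for an OZAWADE change. This shows whether f is negligible, and it picks up rises that were dealt with between visits.

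Do not add a limb for OZAWADE changes to the primary endpoint. Only exposed patients could meet it, and it would rest on open-label attribution, so it would replace one asymmetry with another.

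The cost is one extra model run and one table. Visit and diary blood pressure (9.3.4) and reasons for OZAWADE changes (9.3.7.1) are already foreseen. The sensitivity event is less specific and depends on readings being available. Diary readings follow the visit and may already reflect a change made there, so the result without diary confirmation should be shown as well. The change concerns counting only and proposes nothing about patient care.
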